		improvement	B/C/D and baseline BILAG B to C/D and no BILAG worsening in other organ systems, where worsening is defined as $\geq 1$ new BILAG A or $\geq 2$ new BILAG B	baseline or at the visit remain missing after instrument-level imputation rules are applied, except when the missing is at the baseline (any one or all domains) and the value at the visit is not A or B, then the other nonmissing organ domains will be used to determine the response status.
		No BILAG worsening	No new BILAG A and no $>1$ new BILAG B disease activity score (both compared with baseline), where worsening is defined as $\geq 1$ new BILAG A or $\geq 2$ new BILAG B, both compared with the baseline. The baseline BILAG A improved to BILAG B at the visit will not be considered as the new BILAG B.	Missing if any of 9 domains at baseline or at the visit remains missing after instrument-level imputation rules are applied except when the baseline (any one or all domains) is BILAG A and the value at the visit is missing, then the other nonmissing organ domains will be used to determine the response status.
		Individual Organ Domain Improvement Defined by BILAG	Among patients with BILAG A or B at baseline and able to reduce the baseline BILAG A to B/C/D and BILAG B to C/D for each organ domain, separately.	Missing if baseline or value remains missing after instrument-level imputation rules are applied.
		Individual Organ Domain Worsening Defined by BILAG	Among patients without BILAG A at baseline, an increment of baseline BILAG B/C/D/E to A or baseline BILAG C/D/E to B for each organ domain, separately.	Missing if baseline or value remains missing after instrument-level imputation rules are applied.
Physician's Global Assessment of Disease Activity	The PGA is the physician's assessment of the patient's overall disease activity due to SLE. It is scored using a visual analog scale	PGA score PGA category	Permitted range of values is from 0 to 100 mm. PGA categories are defined as: None (0) = '0 mm', Mild ( $>0$ and $<1.5$ ) = ' $>0$ to $<50$ mm', Moderate ( $\geq 1.5$ to $\leq 2.5$ )	If the visit occurred, data can be carried forward if obtained within 36 days of visit; otherwise missing.

Measure	Description	Variable	Derivation/Comment	Definition of Missing

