(PGA)	where 0 mm indicates no disease activity and 100 mm indicates the most severe disease activity possible. There are benchmarks of 0 (0 mm), 1 (33 mm), 2 (67 mm), and 3 (100 mm) on the line corresponding to no, mild, moderate, and severe SLE disease activity, respectively.		= '≥50 mm to ≤83mm', Severe (>2.5) = '>83mm'.	
		No worsening in PGA	Worsening is defined as an increase of ≥0.3 points (10 mm) from baseline. Therefore, no worsening is defined as any decrease, no change, or <0.3 points (10 mm) increase from baseline.	Missing if baseline or value remains missing after instrument-level imputation rules are applied.
		PGA ≤1	PGA ≤33 mm	Missing if value remains missing at the visit after instrument-level imputation rules are applied.
BICLA	BICLA is a composite index to measure overall improvement in disease activity (BILAG) while ensuring there is no worsening in other organ systems (SLEDAI-2K and PGA)	BICLA	
 
Reduction of all baseline BILAG A to B/C/D and baseline BILAG B to C/D and no BILAG worsening in other organ systems, where worsening is defined as ≥1 new BILAG A or ≥2 new BILAG B
 
No worsening from baseline in SLEDAI-2K, where worsening is defined as an increase from baseline of >0 points in SLEDAI-2K
 
No worsening from baseline in participants' lupus disease activity, where worsening is defined by an increase ≥0.30 points on a 3-point PGA visual analogue scale (VAS).
 
	Missing if any component (BILAG, SLEDAI or PGA) remains missing after each instrument level imputation rule is applied.
Cutaneous Lupus Erythematosus Disease Area and Severity Index (CLASI)	The CLASI is a validated instrument to assess cutaneous manifestations of SLE consisting of 2 scores: 
 
Activity
 
Damage
 
	Total Activity Score	Calculated within tablet system with edit checks; no additional derivation.	Within tablet system: if any item scores, but not all, are missing then impute a score of 0 for the missing item(s). For completely missing questionnaires, data can be carried forward if obtained within 36 days of visit; otherwise missing.

Measure	Description	Variable	Derivation/Comment	Definition of Missing

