**Table JAIM.6.4. Description of Efficacy/Health Outcomes Analyses**

Measure	Variable	Analysis Method	Population	Key Time Point(s) a
SRI-4	Proportion of patients achieving SRI-4 response	Descriptive analysis with observed and NRI	mITT, patients with SLEDAI-2K score of $\geq 4$ at baseline	Week 156 visit
SRI-x (where x is 5, 6, 7, 8)	Proportion of patients achieving SRI-x response	Descriptive analysis with observed and NRI	mITT, patients with SLEDAI-2K score of $\geq x$ at baseline	Week 156 visit
SLEDAI-2K	Change from baseline in mean total SLEDAI-2K through Week 156	MMRM	mITT	Week 156 visit
	Proportion of patients achieving reduction of $\geq 4$ points from baseline	Descriptive analysis with observed and NRI	mITT, patients with SLEDAI-2K score $\geq 4$ at baseline	Week 156 visit
	Proportion of patients with improvement in each SLEDAI-2K individual organ systems vs baseline	Descriptive analysis with observed and NRI	mITT, patients with SLEDAI-2K score $> 0$ within the organ domain at baseline	Week 156 visit
	Proportion of patients with worsening in each SLEDAI-2K individual organ system vs baseline	Descriptive analysis with observed and NRI	mITT, patients with at least 1 SLEDAI-2K item = 0 in the organ domain at baseline	Week 156 visit
BILAG	Proportion of patients with no new BILAG A and no more than 1 new BILAG B disease activity score (compared with baseline)	Descriptive analysis with observed and NRI	mITT	Week 156 visit
	Proportion of patients with improvement in each BILAG individual organ system vs baseline	Descriptive analysis with observed and NRI	mITT, patients with BILAG A or B in the organ domain at baseline	Week 156 visit
	Proportion of patients with worsening in each BILAG individual organ system vs baseline	Descriptive analysis with observed and NRI	mITT, patients without BILAG A in the organ domain at baseline	Week 156 visit
PGA	Proportion of patients with no worsening in PGA (compared with baseline)	Descriptive analysis with observed and NRI	mITT	Week 156 visit
	Change from baseline in PGA score over time through Week 156	MMRM	mITT	Week 156 visit
BICLA	Proportion of patients achieving BICLA response	Descriptive analysis with observed and NRI	mITT	Week 156 visit
28 Tender/Swollen Joint Count	Change from baseline in tender joint count	MMRM	mITT	Week 156 visit
	Change from baseline in swollen joint count	MMRM	mITT	Week 156 visit

Measure	Variable	Analysis Method	Population	Key Time Point(s) a

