CLASI Activity Score	The proportion of patients with $\geq 50\%$ reduction from baseline in total activity score	Descriptive analysis with observed and NRI	mITT – patients with CLASI total activity score $\geq 10$ at baseline	Week 156 visit
SFI	Annualized severe flare rate	Descriptive analysis with observed rate	mITT	Week 0 to Week 156 visit
	Annualized severe flare rate	Descriptive analysis with observed rate	mITT	Week 0 to Week 156 visit
	Annualized severe flare rate	Descriptive analysis with observed rate	mITT	Week 0 to Week 156 visit
SLICC/ACR Damage Index Score	Change from baseline in SLICC/ACR Damage Index	Descriptive analysis with observed and mLOCF	mITT	Week 156 visit
LLDAS	Proportion of patients who achieve a LLDAS	Descriptive analysis with observed and NRI	mITT, patients with SLEDAI score of $\geq 4$ at baseline	Week 156 visit
Corticosteroid Sparing	Change from baseline in prednisone dose	MMRM	mITT	Week 156 visit
Worst Pain NRS	Change from baseline in Worst Pain NRS	MMRM	mITT	Week 156 visit
FACIT-Fatigue	Change from baseline in FACIT-Fatigue total score	MMRM	mITT	Week 156 visit
Worst Fatigue NRS	Change from baseline in Worst Fatigue NRS	MMRM	mITT	Week 156 visit
Worst Joint Pain	Change from baseline in Worst Joint Pain NRS	MMRM	mITT	Week 156 visit
Patient Global Impression of Severity	Change from baseline in Patient Global Impression of Severity	MMRM	mITT	Week 156 visit
SF-36 V2 acute	Change from baseline in mental component score (MCS)	MMRM	mITT	Week 156 visit
	Change from baseline in physical component score (PCS)	MMRM	mITT	Week 156 visit
	Change from baseline in domain scores SF-36 health survey version 2 acute	MMRM	mITT	Week 156 visit
EQ-5D-5L	Change from baseline in EQ-5D-5L US/UK population-based index scores and VAS.	MMRM	mITT	Week 156 visit
	Proportion of patients with no problem in each EQ-5D-5L item score	Descriptive analysis with observed and NRI	mITT	Week 156 visit

Measure	Variable	Analysis Method	Population	Key Time Point(s) a
WPAI-Lupus	Change from baseline in WPAI-Lupus	MMRM	For absenteeism score, presenteeism score, and work productivity loss score, population is a subset of mITT that includes patients who had an employment status of Yes at baseline. For activity impairment score, use mITT population	Week 156 visit

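### BICLA is analysed in the whole mITT population, so under the written rule a patient with no BILAG A or B at baseline is a responder simply by not worsening

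*SAP*

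**What the plan says.** Table JAIM.6.4 analyses "Proportion of patients achieving BICLA response" descriptively, with observed data and with non-responder imputation, in mITT. Table JAIM.6.2 defines mITT by having taken at least one dose in JAIM, with one site removed; disease activity plays no part.

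Table JAIM.6.3 gives the purpose as "BICLA is a composite index to measure overall improvement in disease activity (BILAG"), with SLEDAI-2K and PGA guarding against worsening elsewhere. The BILAG component is "Reduction of all baseline BILAG A to B/C/D and baseline BILAG B to C/D and no BILAG worsening in other organ systems". The threshold for that last condition follows in the same entry: "where worsening is defined as ≥1 new BILAG A or ≥2 new BILAG B". The other two components are no rise in SLEDAI-2K and no PGA increase of 0.30 points or more. Nothing requires an A or B at baseline.

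In the same table the organ-level BILAG improvement variable begins "Among patients with BILAG A or B at baseline and able to reduce the baseline BILAG A to B/C/D and BILAG B to C/D". Its row in Table JAIM.6.4 repeats the limit: "mITT, patients with BILAG A or B in the organ domain at baseline".

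**The concern.** The population and the response rule do not fit the stated purpose. If a patient has no A or B to bring down, the improvement component tests nothing and the endpoint becomes one of not worsening. The reported proportion then mixes patients who improved with patients who merely stayed stable, and the table would not show how many of each there are.

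The switch arms are where this is most likely. Under SAP 6.3 their baseline is the last assessment before the first baricitinib dose at JAIM Week 0, which follows 52 weeks in the originating study (SAP 5.1). Protocol 6.1 sets no disease-activity threshold for entering JAIM. The continuing arms use the originating-study baseline. The entry criteria of those studies are not in the documents, so the affected share there may be zero.

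**Working it through.** **1. What the rule implies.** A patient with only B scores at baseline has no A to reduce. For that patient to be able to respond at all, the absent category must count as met. Applied consistently, a patient with neither A nor B meets the reduction clause automatically. The missing-data rule for BILAG improvement points the same way, though only indirectly: a missing baseline ("any one or all domains) and the value at the visit is not A or B") does not prevent response from being determined.

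**2. The literal rule on simple profiles** (all other organ systems unchanged):

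| Baseline BILAG | Visit BILAG | SLEDAI-2K change | PGA change | BICLA responder |
|---|---|---|---|---|
| No A or B | No A or B | 0 | 0 | Yes |
| No A or B | One new B | 0 | 0 | Yes |
| One B | Same B | 0 | 0 | No |
| No A or B | No A or B | +1 | 0 | No |

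The second and third patients end in the same BILAG state, yet the one who got worse is the responder. Under non-responder imputation the patient must also have stayed on treatment without prohibited medication.

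**3. Effect on the reported rate.** The plan states no BICLA rate, so there is no figure to reproduce. Let q be the share with no baseline A or B, w the rate at which they count as responders, and r the rate among patients with an A or B.

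Reported rate = (1 − q)·r + q·w, so the shift against r is q·(w − r).

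None of the three is in the documents. Assuming w = 40–90% and r = 40–60%:

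- q = 0: no shift.
- q = 5%: 0.05 × (40 − 60) = −1.0 to 0.05 × (90 − 40) = +2.5 points.
- q = 10%: −2.0 to +5.0 points.
- q = 20%: −4.0 to +10.0 points.

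One worked case: q = 20%, r = 40%, w = 70% gives 0.8 × 40 + 0.2 × 70 = 46% reported, against 40% among patients who had something to improve. A more extreme assumption (q = 50%, r = 30%, w = 85%) gives 0.5 × 55 = 27.5 points.

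The nearest figure in the documents is the Phase 2 placebo SRI-4 rate of 47.6% at Week 24 (Protocol 3.1). It does not give q: it comes from another study, and SRI-4 requires no fall in BILAG.

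**4. Precision cost of restricting the denominator.** Planned enrolment is 1100 (SAP 5.2). Assume one third come from placebo, split 1:1: 1100/3/2 ≈ 183 per switch arm. At a 50% rate the Wilson 95% half-width is 1.96 / (2·√(n + 1.96²)). With 0, 10 and 20% excluded:

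| Still evaluable (assumed) | n | Half-width, points |
|---|---|---|
| All, at entry | 183 / 165 / 146 | 7.17 / 7.54 / 8.01 |
| 80% | 146 / 132 / 117 | 8.01 / 8.41 / 8.91 |
| 50% | 92 / 82 / 73 | 10.01 / 10.58 / 11.18 |

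The largest widening here is 11.18 − 10.01 = 1.17 points. If half were excluded and half remained evaluable, n would be 46 and the half-width about 13.9, a widening of about 3.9.

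**The case against.** The best counter-argument is that the SAP never says in words how a patient with no baseline A or B is classified. Automatic response is an inference, and a programmer might code such patients otherwise. That is true, but it is the only reading under which B-only patients can respond, and an unstated case that can be coded two ways needs settling anyway.

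The comparison with neighbouring rows also needs care. The SRI, SLEDAI-2K reduction and organ-improvement rows mainly drop patients who could not respond, which is the opposite problem. The CLASI threshold comes from the protocol endpoint. The LLDAS row ("mITT, patients with SLEDAI score of" at least 4) still admits a patient at exactly 4, who already meets the SLEDAI-2K ceiling. The EQ-5D-5L no-problem items are analysed in plain mITT, but they describe a state and are not presented as improvement. The comparison that carries weight is the organ-level BILAG variable, where the same reduction wording is explicitly limited.

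The tolerance of one new B applies to every patient and would survive the fix. It illustrates the problem and is not the defect itself. Separate rows for organ-level BILAG improvement and for absence of BILAG worsening are planned and give part of the picture, but not the number of patients with no A or B in any domain. Finally, no affected patient has been shown to exist. That stands, and it limits what can be said about size.

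**Conclusion.** The concern holds, as a minor point. The written rule and the chosen population together let stability count as BICLA response in patients without baseline BILAG A or B, and nothing elsewhere in the SAP or protocol corrects this. The size and the sign of the effect are unknown; every figure for the shift above rests on assumed values of q, w and r, and the effect is nil if q is zero. Little depends on the result: BICLA was added in SAP version 3 (Revision History), is not an objective or endpoint in Table JAIM.4.1, is summarised descriptively, and has no planned comparison between arms.

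**What to change.** In Table JAIM.6.4, change the BICLA population to mITT patients with at least one BILAG A or B at baseline, and report the number excluded in each arm. This matches the organ-level rule. Patients whose baseline BILAG is wholly missing would then fall outside the row, which should be said.

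If plain mITT is preferred, state in Table JAIM.6.3 that patients with no baseline A or B count as responders when they do not worsen, and show their number per arm. This keeps the denominator and removes the doubt, but the proportion still mixes two outcomes.

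The cost is one table cell and one count per arm. Appendix 2 already plans baseline A or B involvement by organ system, so an any-domain flag is a small derivation. The restriction gives up some precision: at most about 1.2 points of half-width if up to 20% are excluded, more if the share is larger. Later intervals are smaller anyway, because discontinued patients leave them (SAP 6.4.2). Neither option removes the difference in baseline between continuing and switching arms.

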5.1. Overall Design

Study I4V-MC-JAIM [JAIM] is a Phase 3, multicenter, randomized, outpatient, long term extension trial to evaluate the long-term safety and efficacy of baricitinib in eligible patients with SLE who have completed the treatment period in an originating study (such as, Study I4V-MC-JAHZ [JAHZ] or Study I4V-MC-JAIA [JAIA]).

Figure JAIM.1 illustrates the study design.

The study consists of 3 periods:

[figure not shown]
Screening Period: Screening for JAIM (Week 0, Visit 1) should occur during the last visit of the originating study. However, in particular circumstances, this duration may be extended after consultation with the sponsor.

Treatment Period: Patients randomized to active treatment, baricitinib 4-mg daily or baricitinib 2-mg daily, during the originating studies will continue on the same, blinded dose of baricitinib in Study JAIM. Patients randomized to placebo during the originating studies will be randomized 1:1 to receive blinded baricitinib 2-mg or 4-mg daily during Study JAIM. Randomization will be stratified by corticosteroid dose on the day of randomization (<10 mg/day; ≥10 mg/day of prednisone or equivalent), and region (defined in the statistical analysis plan [SAP]). Patients originally randomized to active treatment in originating study with renal impairment at baseline of the originating study will not receive doses higher than 2-mg baricitinib QD. Patients randomized to placebo in the originating study with renal impairment (defined as estimated glomerular filtration rate [eGFR] <60 mL/min/1.73 m²) at the time of randomization to JAIM (assessed by the most recent eGFR from the originating study) will receive 2-mg baricitinib QD. The treatment period will last up to 156 weeks from enrollment into Study JAIM.

Patients may continue to receive the background standard therapies for SLE, including a corticosteroid, a single antimalarial, and/or a single immunosuppressant, that they were receiving at completion of the originating study.

Throughout the trial, investigators should continue to assess individual benefit-risk for patients to remain in the trial and should consider discontinuing patients if sufficient clinical benefit is not observed with protocol-permitted treatments.

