**Table JAIM.4.1. Primary and Secondary Objectives**

Objectives	Endpoints (Variables)
Primary	
To evaluate the long-term safety and tolerability of baricitinib in patients with SLE.	Safety and tolerability assessments will include: 
 
• Proportion of patients with treatment-emergent adverse events (TEAEs), adverse events of special interest (AESIs), and serious adverse events (SAEs).
 
• Proportion of patients with temporary investigational product interruptions and permanent discontinuations.
 

Secondary	
To evaluate the long-term effect of baricitinib 4-mg or 2-mg QD and background standard-of-care therapy on SLE disease activity.	
 
• Proportion of patients achieving SRI-4 response through Week 156, defined as:               
 
○ Reduction of <math>\geq 4</math> points from baseline in SLEDAI-2K score; and
 
○ No new British Isles Lupus Assessment Group (BILAG) A or* no more than 1 new BILAG B disease activity score; and
 
○ No worsening (defined as an increase of <math>\geq 0.3</math> points [10 mm] from baseline) in the Physician's Global Assessment of Disease Activity.
 
 
 
• Proportion of patients achieving an SRI-5, -6, -7, or -8 response through Week 156.
 
• Proportion of patients achieving an LLDAS response through Week 156.
 
• Change from baseline in mean total SLEDAI-2K scores through Week 156.
 
• Change from baseline in Physician's Global Disease Activity score through Week 156.
 

To evaluate the long-term corticosteroid sparing effect of baricitinib 4-mg or 2-mg QD.	Change from baseline in prednisone dose through Week 156.

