**Table JAIM.6.2. Analysis Populations**

Population	Description
Entered Population	
Definition: All patients who signed informed consent form in Study JAIM
 
Purpose: Used for patient allocation summary
 
Treatment Groups: As given in Table JAIM.6.1

Randomized Population	
Definition: All patients who were randomized/assigned in Study JAIM (Note: patients randomized to active treatment during the originating study will be assigned to the same, blinded dose of baricitinib in Study JAIM; patients randomized to placebo during the originating studies will be randomized 1:1 to blinded baricitinib treatment of 2 mg once daily (QD) or 4 mg QD in Study JAIM)
 
Purpose: Used for patient allocation summary
 
Treatment Groups: As given in Table JAIM.6.1

Modified Intent-to-Treat (mITT) Population	
Definition: All participating patients, excluding those from PPD, who receive at least 1 dose of study treatment in Study JAIM (regardless if the patient does not receive the correct treatment, or otherwise does not follow the protocol)
 
Purpose: Used for efficacy and health outcomes related analyses
 
Treatment Groups: As given in Table JAIM.6.1

Safety Population	
Definition: For the purpose of analysis of Study JAIM alone, the safety population is defined as all patients, excluding those from PPD, who receive at least 1 dose of investigational product in Study JAIM and who did not discontinue from the study for the reason 'Lost to Follow-up' at the first postbaseline visit
 
Purpose: Used for safety analyses
 
Treatment Groups: Safety analyses will be analyzed according to 5 treatment groups as defined in Table JAIM.6.1

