## Summary Tables Related to Patient Characteristics

Variable	Continuous Summary	Categorical Summary a	Included in Interim 1 Analysis/ Derivation
Corticosteroid use d . See Section 6.10.1 for details of prednisone (or equivalent) baseline dose	Yes	Yes, No	Yes
		<10 mg/day or ≥10 mg/day	Yes
		≤7.5 mg/day or >7.5 mg/day	Yes
Immunosuppressant d use at baseline	No	Yes, No	Yes
Mycophenolate mofetil use at baseline	No	Yes, No	Yes
Azathioprine d use at baseline	No	Yes, No	Yes
Methotrexate d use at baseline	No	Yes, No	Yes
Antimalarial d use at baseline	No	Yes, No	Yes
Hydroxychloroquine d use at baseline	No	Yes, No	Yes
NSAID d use at baseline	No	Yes, No	Yes
Statin use at baseline	No	Yes, No	Yes
Other Baseline Measures			
Baseline SF-36 PCS, MCS	Yes	None	No
Baseline WPAI Lupus – Employment status	No	Yes, No	No
Baseline WPAI Lupus – Absenteeism score, Presenteeism Score, Work Productivity Loss Score, Activity Impairment Score	Yes g	None	No
EQ-5D-5L VAS and Item scores	Yes	None	No
FACIT-Fatigue Total score	Yes	None	No
Worst Pain NRS	Yes	None	No
Worst Joint Pain NRS	Yes	None	No
Worst Fatigue NRS	Yes	None	No

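### The only corticosteroid-sparing endpoint averages dose change over all mITT patients, so it measures net steroid use and understates the reduction among patients who had a dose to reduce

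*SAP*

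**What the plan says.** SAP Table JAIM.4.1 gives the objective as "To evaluate the long-term corticosteroid sparing effect of baricitinib 4-mg or 2-mg QD" and lists one endpoint for it, "Change from baseline in prednisone dose through Week 156". The Corticosteroid Sparing row of Table JAIM.6.4 names the variable as "Change from baseline in prednisone dose" and assigns it to MMRM, with Week 156 as the key time point. The population entry is mITT and nothing more.

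Table JAIM.6.2 defines mITT as patients "who receive at least 1 dose of study treatment in Study JAIM", less those from one excluded site. Baseline steroid use plays no part in the definition.

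A corticosteroid is not mandatory. Protocol Section 5.1 lets patients continue background therapy "including a corticosteroid, a single antimalarial, and/or a single immunosuppressant, that they were receiving at completion of the originating study". SAP Appendix 2 tabulates baseline corticosteroid use as Yes or No and adds "See Section 6.10.1 for details of prednisone (or equivalent) baseline dose". Section 6.10.1 takes the baseline as the total daily prednisone-equivalent dose on the day before the first baricitinib dose. It does not say how a patient on no steroid is coded. Table JAIM.6.3 sets no minimum data requirement for steroid dose.

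Protocol Section 7.7 permits both tapering and increases of corticosteroid during the study.

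**The concern.** Sparing presupposes a dose that can be reduced. A patient who starts at 0 mg/day can stay there or go up, and so contributes zero or a positive number to the mean. Averaging such patients with steroid users gives the change in steroid use across the treated population. That is a different quantity from the reduction achieved by patients taking the drug the objective is about.

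Nothing else specified in the two documents isolates baseline users. Protocol Section 10.3.5 says only that subgroup analyses may be done if needed. The SAP restricts between-group inference, so the reported within-arm mean and its interval are the main output for this objective. A reader who takes that mean as the typical reduction among steroid users would get too small a number, and could not correct it reliably because new starts among non-users are mixed in.

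**Working it through.** **Inputs from the documents.** Population mITT, method MMRM on change from baseline (SAP Table JAIM.6.4, Section 6.4). Covariates include baseline value, baseline value by visit, and baseline corticosteroid stratum (<10 or ≥10 mg/day). Neither document gives the share of non-users, an expected dose reduction or a standard deviation, so there is no planned figure to reproduce. Everything below rests on stated assumptions, and a non-user's baseline is taken as 0.

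**Step 1: the mean.** Let f be the share of an arm on no steroid at baseline.

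Mean change (all mITT) = (1 − f) × mean change in users + f × mean change in non-users, where the last mean is ≥ 0.

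Assume users fall by 3 mg/day and non-users stay at 0:

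| f | Calculation | Reported mean (mg/day) |
|---|---|---|
| 20% | 0.8 × (−3) | −2.4 |
| 40% | 0.6 × (−3) | −1.8 |
| 50% | 0.5 × (−3) | −1.5 |

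If, in addition, non-users making up one tenth of the whole arm start 5 mg/day, each figure moves up by 0.10 × 5 = 0.5 mg/day, to −1.9, −1.3 and −1.0.

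**Step 2: do the covariates remove this?** A single-visit simulation used baseline dose and the <10/≥10 stratum as covariates. User doses were drawn with mean 10 mg/day, users fell by about 30% of their dose, and non-users stayed at 0. LS means were taken at the observed covariate margins:

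| Users | Mean change in users | Adjusted LS mean, all | Ratio |
|---|---|---|---|
| 50% | −2.915 | −1.460 | 0.50 |
| 70% | −2.919 | −2.041 | 0.70 |
| 90% | −2.926 | −2.634 | 0.90 |

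The ratio equals the share of users, so within an arm the adjustment leaves the dilution in place.

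**Step 3: the within-arm test against zero.** With N patients in an arm, a fall of d in users with standard deviation SD, and non-users fixed at 0, the variance over all patients is (1 − f)SD² + f(1 − f)d². Therefore

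z(all) / z(users only) = 1 / √(1 + f·d²/SD²).

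With SD = 6 mg/day (assumed):
- d = 3: f = 20% gives 1/√1.05 = 0.98, and f = 40% gives 1/√1.10 = 0.95.
- d = 2, f = 10%: 1/√(1 + 0.1 × 4/36) = 0.99.
- d = 4, f = 50%: 1/√(1 + 0.5 × 16/36) = 0.91.

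Over these ranges the test statistic falls by 1% to 9%, while the mean falls by 10% to 50%.

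**The case against.** **Net dose change is a deliberate and defensible choice.** It counts steroid starts, which a users-only analysis hides. Protocol amendment (a) removed two categorical endpoints confined to patients on steroid at baseline, as unsuited to so long a study, and kept dose change. This stands, and it is why the all-mITT analysis should stay. The stated reason concerned the categorical form, however, and does not argue against looking at users.

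**The share of non-users will be visible.** Baseline use is tabulated by arm, so a reader could rescale the mean. That works only if no non-user starts a steroid, and no summary of new starts by baseline use is specified.

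**A users-only analysis has its own bias.** Selecting on a baseline dose above zero in an extension without a control arm permits regression to the mean, which flatters the apparent reduction. This stands, and it rules out users-only as the sole analysis.

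**Efficacy is secondary here.** SAP Section 6.11.2 says efficacy is not a primary outcome. That limits the weight of the point. Exploratory and integrated plans are separate documents and may cover users, but they are not available here.

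A reader might infer two stronger points that the documents do not support:

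- **That the row breaks the table's own rule.** Entries such as "mITT – patients with CLASI total activity score" limit the population to patients able to improve. Those rows (SRI, organ-domain improvement, CLASI, LLDAS) are responder proportions. Continuous change rows, including SLEDAI-2K total, joint counts and the pain and fatigue scales, use plain mITT, although a patient with no swollen joints also cannot improve. The three WPAI work scores are restricted because they are undefined without employment. The steroid row follows the table's convention.
- **That arms with equal reductions among users would report different results.** Baselines in the continuing and switching arms lie about a year apart, so f may differ. But the model adjusts for baseline dose. In a two-arm, single-visit simulation with f = 20% and 40%, the raw gap of 0.60 mg/day fell to about 0.23 with a constant 3 mg fall in users (user doses averaging 10 mg/day), and to about zero with a fall proportional to dose. SAP Section 6.1 also plans no inferential comparison between arms.

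**Conclusion.** The point holds as a matter of what is estimated. The planned mean is a valid estimate of net steroid use in treated patients, and it would go too far to call it an invalid analysis. It understates the reduction among baseline users by approximately the share of non-users, and by more if any of them start a steroid. The direction follows from the design as long as non-users are present and coded 0. The amount cannot be fixed from the documents: the 3 mg/day fall, the values of f and the SD of 6 mg/day are illustrations.

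The zero coding is itself an inference. The <10 mg/day stratum and the absence of a minimum data requirement both point to 0. If non-users were instead coded as missing, SAP Section 6.1 means no change would be calculated for them, and the analysis would become users-only without saying so.

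This is a low-cost improvement to a secondary objective. It does not bear on the primary safety outcome.

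**What to change.** In SAP Table JAIM.6.4:

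1. Keep the all-mITT MMRM of change in prednisone dose and label it as net steroid use.
2. Add a pre-specified analysis of the same variable in mITT patients with a baseline prednisone-equivalent dose above 0 mg/day, giving n per arm.
3. Report beside it, per arm, the number and percentage of baseline non-users who start a corticosteroid.

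In Section 6.10.1, state that a patient taking no corticosteroid has a baseline dose of 0 mg/day.

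The cost is one further run of the planned model and one count table. Section 6.10.1 already derives daily prednisone-equivalent doses, so nothing new is collected. The users-only analysis has a smaller n and is open to regression to the mean, so the SAP should say that it is to be read together with the all-mITT result and does not replace it.
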